8.7 Statistical Analyses

8.7.1 Demographics and Baseline Characteristics

Demographic and baseline characteristics (i.e., age at screening, gender, weight, height, body mass index (BMI), race, ethnicity, medical history, physical examination, prior medications) will be listed for individual subjects and summarized by treatment group using summary statistics for continuous variables and frequency distributions for discrete variables.

8.7.2 Prior and Concomitant Medications

Concomitant medications will be coded using the World Health Organization Drug Dictionary and will be summarized by treatment group and WHO Anatomical Therapeutic Chemical (ATC) class and medication name. These summaries will present the number and percentage of subjects using each medication.

8.7.3 Completion of the Study and Withdrawals

Withdrawals and the reason for withdrawal (i.e., AE(s), protocol non-compliance, requirement for an unacceptable concomitant medication, lost to follow-up, failed to return, voluntary withdrawal, and other reasons) will be listed. The number and percentage of subjects who complete the study will be summarized. The number and percentage of subjects who withdraw from the study will be tabulated by treatment group at time of withdrawal.

8.7.4 Protocol Deviations

Protocol deviations will be listed and categorized (i.e., Inclusion/Exclusion Criteria, Randomization, Study Procedures, Missed Study Visit, Visit out of Study Window, Informed Consent, Safety Reporting, Study Drug Administration, Study Drug Accountability, and Other) and summarized based on these categories.

8.7.5 Safety Analysis

8.7.6.1 Adverse Events

Adverse events (AE) will be classified into standard terminology (preferred term and system organ class) using the Medical Dictionary for Regulatory Activities. The severity of each adverse event will be graded as 1) mild, 2) moderate, 3) severe, or 4) life-threatening, according to the Common Terminology Criteria for Adverse Events (CTCAE) version 4.0.

In addition, all adverse events will be classified as to whether the relationship to study drug was 1) None, 2) Unlikely, 3) Possible, or 4) Probable and followed to resolution or until the adverse event or condition has stabilized.

The incidence and duration of treatment-emergent adverse events (TEAEs) will be summarized by treatment group according to MedDRA-preferred term and MedDRA system organ class term. An AE will be considered treatment emergent if the onset date and time occur on or after the recorded clock time of study drug administration. Tabulations of adverse events by severity grade and causal relationship to study drug (related, unrelated) will be provided.

For reporting purposes, AEs assigned a relationship to study drug of "Possible" and "Probable" will be classified as related to study drug. AEs assigned a relationship to study drug of "Unlikely" or "None" will be classified as not related to study drug.

The number and percentage of subjects with reported serious adverse experiences (SAEs) and subjects who withdrew due to an AE will be tabulated by treatment group.

All adverse events will be presented in by-subject listings by reported verbatim term and MedDRA-preferred term, MedDRA system organ class, start and stop date and time, study day, duration, severity, relationship to study drug, seriousness, and outcome. All reported serious adverse events will also be displayed in by-subject listings.

8.7.6.2 Oral Cavity Assessment

Oral cavity assessment (hard and soft tissues) findings will be documented at Screening and at each protocol-specified study visit.

Clinically significant examination findings identified at Screening will be added to the subject's Medical History.

After study drug administration clinically significant changes in the oral cavity assessment will be recorded as AEs and these TEAEs will be summarized by treatment group for each of the protocol specified assessments by calculating the number and proportion of subjects who develop clinically significant findings in the oral cavity after study drug administration.

8.7.6.3 Targeted Physical Examination

Targeted physical examination (general, extraoral, head and neck) findings will be documented at Baseline and at each protocol-specified study visit.

Prior to administration of study drug, clinically significant examination findings will be added to the subject's Medical History.

After study drug administration clinically significant changes in the targeted physical examination will be recorded as AEs.

8.7.6.4 Vital Signs

Vital sign results (blood pressure, heart rate and temperature) will be summarized at Visit 1 (Day -30 to Day -2) and Visit 3-5 pre- and post-study drug administration for each treatment group by calculating the mean, median, standard deviation, and range. Mean change from baseline will also be presented where baseline is defined as prior to study drug administration at Visit 3-5 for each study visit.

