Study Design:	
A single-blind, randomized, placebo-controlled Phase 2 study to evaluate the safety and oral microbiology of C16G2 Varnish application in male and female dental subjects 12-75 years of age. This multi-center study will evaluate multiple study drug administrations of C16G2 Varnish or Placebo.
 
Before dosing of study drug, eligible subjects will undergo professional dental prophylaxis 2-7 days prior to the first study drug administration. Subjects will receive three study drug applications over approximately 5 days. Study drug will be applied with a small brush typically used in dental varnish administration. To evaluate the durability of S. mutans suppression, study subjects will be followed for microbiology for 1 month after the last study drug administration.
 
Clinic visits include Visit 1 (Screening/Days -30 to -1), Visit 2 (Prophylaxis/Day -7 to -2), Visits 3-5 (Confirmation of Eligibility and Baseline (V3 ONLY) & Study Drug Administration), Follow-up Visits 6-8 (Safety and Microbiology) and Follow-up Visits 9 and 10 (Microbiology only). Dosing Visits 4 and 5 will occur 24-48 hours post-previous dosing visit.
 
Enrolled subjects will be assessed for safety and microbiology parameters. For details on study schedules including dosing and microbiology information refer to Appendix A. Details on study assessments & procedures are provided in Appendix B. For microbiology assessments refer to Appendix C.

Objectives:	
Primary Objective
 
 • To evaluate the safety and tolerability of multiple C16G2 Varnish administrations in adolescent and adult dental subjects 
Secondary Objectives
 
 • To assess the targeted antimicrobial activity of C16G2 Varnish administration as measured by a reduction in Streptococcus mutans in saliva and dental plaque • To assess total bacteria in saliva and dental plaque post study drug administration
Subject Population:	Approximately 33 male and female subjects 12-75 years of age, inclusive at the time the Assent and/or Informed Consent Form is signed.
Duration of Study:	All subjects will be followed for safety and microbiology for up to 1 month after first study drug administration.

	Estimated duration of study from first subject in (FSI) to last subject out (LSO) is approximately 3 months.																				

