2. STUDY OBJECTIVES

Primary Objective

- To evaluate the safety and tolerability of multiple C16G2 Varnish administrations in adolescent and adult dental subjects

Secondary Objectives

- To assess the targeted antimicrobial activity of C16G2 Varnish applications as measured by a reduction in *Streptococcus mutans* in saliva and dental plaque
- To assess total bacteria in saliva and dental plaque post-study drug administration

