6.3.6.3 Clinic Visit 3 (Baseline, Day 0)

Subjects will be scheduled for this visit between 6AM and 10AM. Subjects should not be exposed to study drug if they present with any disruption or loss of integrity in the oral cavity mucosa, gingiva or have lip lesions, (e.g. aphthous stomatitis, active herpetic sores, cheek bites, severely chapped or cracked lips, etc.).

Pre-Dose

- Confirmation of eligibility
- Medical/Dental and Surgical History & Concurrent Illness Update
- Concomitant Medications Update
- Urine Pregnancy Test (females of childbearing potential only)
- Oral Cavity Assessment
- Targeted Physical Exam (general, extraoral, head & neck)
- Vital Signs (blood pressure, heart rate, temperature) taken in supine or sitting position
- Microbiology (stimulated saliva and dental plaque collection)
Note: Samples need to be obtained prior to oral hygiene
- Randomization
- Oral Hygiene (including brushing and flossing will be conducted at the clinic prior to study drug administration)

Study Drug Administration:

Instructions for the preparation of C16G2 Varnish or Placebo are provided in the Study Manual. Instructions for the application of study drug are provided in Appendix G.

- At Visit 3/Day 0, subjects will receive a single study drug administration. Subjects will have C16G2 Varnish or Placebo applied to all tooth surfaces.
Note: C16G2 Varnish or Placebo will not be actively removed, but remain on the subject's teeth until removed through normal wear and mastication after discharge

Post-Dose

- Photographic imaging immediately after study drug application (see instructions in Appendix H)
- Oral Cavity Assessment (hard and soft tissues)
- Vital Signs (blood pressure, heart rate, temperature) taken in supine or sitting position 1 hour (\pm 15 minutes) post study drug administration
- Subjects will not eat, swish, or drink anything besides plain water from study drug administration to one hour after study drug application. In addition, subjects will be advised to relax their jaws and to not grind their teeth. Subjects will be supervised to ensure compliance
- Adverse Events
- Discharge

6.3.6.4 Clinic Visit 4 (24-48 hrs Post Visit 3) & Visit 5 (24-48 hrs Post Visit 4)

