8. STATISTICAL CONSIDERATIONS

8.1 General Considerations

Protocol C3J16-V204-00 is a phase 2, single-blind, randomized, placebo controlled study designed to evaluate the safety and microbiological activity of C16G2 Varnish applied directly to the tooth surface. Study subjects will receive a single C16G2 Varnish or Placebo administration on six separate days. The study will evaluate 27.2 mg and potentially 13.6 mg and/or 54.4 mg C16G2 Varnish or Placebo administrations.

The objectives of the study are to evaluate the safety of multiple C16G2 Varnish or Placebo administration in subjects 12-75 years of age, to assess the targeted antimicrobial activity of C16G2 Varnish or Placebo as measured by a reduction in the number of *Streptococcus mutans* in saliva and dental plaque, and to assess total bacteria in stimulated saliva and dental plaque.

For the summary table presentations, data will be summarized in tabular format by treatment group. All statistical analysis will be descriptive in nature. Descriptive summary statistics will include N, mean, standard deviation, median, range (minimum and maximum) for continuous variables, and frequency counts and percent for categorical variables.

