9.3.2 Withdrawal of Subjects

Any subject may choose to withdraw from the study for any reason and at any time. The Investigator will withdraw any subject if it is not in the subject's best interest to continue or the subject is not compliant with study assessments. When a subject is withdrawn from the study (regardless of the reason), the date and reason will be recorded. In addition, the following evaluations will be performed, if feasible and if subject is withdrawn within the safety evaluation period defined in this protocol:

- Concomitant Medication Update
- Adverse events
- Oral cavity assessment
- Targeted physical exam
- Vital Signs
- Microbiology (dental plaque and stimulated saliva)

In addition, subjects may choose to withdraw authorization to use and disclose their protected health information (PHI) as defined by the Health Insurance Portability and Accountability Act of 1996 (HIPAA). Such withdrawal of authorization must be made to the Investigator in writing. Any PHI collected by the Investigator or Sponsor prior to the date of such withdrawal will continue to be used and disclosed.

Subjects may be removed from the study if one or more of the following events occur:

- Significant protocol violation on the part of the Investigator;
- Failure of subject to meet the study entrance criteria;

- Significant noncompliance on the part of the subject with study procedures;
- Withdrawal of consent (refusal of the subject to continue treatment or assessments);
- Develops medical condition, taking a medication which could affect study outcome (e.g., antibiotic);
- Due to adverse event or unacceptable toxicity;
- Decision by the Investigator that termination is in the subject's best medical interest;
- Unrelated medical illness or complication;
- Lost to follow up.

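### Vital-sign change is measured from each visit's own pre-dose reading, so no within-subject change since the first dose is planned at Visits 4 and 5 or at withdrawal

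*Combined protocol and SAP*

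**What the plan says.** Section 8.7.6.4 (Vital Signs) plans two displays. The first is of raw values by treatment group, "summarized at Visit 1 (Day -30 to Day -2) and Visit 3-5 pre- and post-study drug administration", with mean, median, standard deviation and range. The second is mean change from baseline, where "baseline is defined as prior to study drug administration at Visit 3-5 for each study visit".

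Elsewhere the word baseline mostly points to one visit. The synopsis (Study Design) has "Confirmation of Eligibility and Baseline (V3 ONLY", and Section 6.3.6.3 is headed "Clinic Visit 3 (Baseline, Day 0". The overview in Section 3 is looser: it lists baseline among the activities of Visits 3-5 without that restriction.

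Vital signs are taken before and about one hour after application at Visits 3, 4 and 5 (Sections 6.3.6.3 and 6.3.6.4, Appendix B). None are scheduled at Visits 6-8. They are also on the list in Section 9.3.2 for subjects who leave, where "the following evaluations will be performed, if feasible and if subject is withdrawn within the safety evaluation period", and on the exit-examination list in Section 9.3.3.

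The primary objective in Section 2 is "To evaluate the safety and tolerability of multiple C16G2 Varnish administrations in adolescent and adult dental subjects".

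**The concern.** A baseline that restarts at each visit answers one question: what happens in the hour after an application. It does not answer whether a subject's blood pressure, heart rate or temperature has moved since before any study drug was given. By the visit windows, the Visit 4 pre-dose reading falls 24-48 hours after the first dose and the Visit 5 pre-dose reading 48-96 hours after it. A shift that develops between visits becomes part of the next baseline and disappears from the change score.

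For subjects who complete dosing, Visits 4 and 5 are the only scheduled occasions after Visit 3 on which such a shift could be seen. A reading at withdrawal or termination on a non-dosing day has no same-visit pre-dose value, so no change is defined for it. The raw summary is limited to Visits 1 and 3-5 and does not include it either. Section 8.7.6.4 mentions no by-subject listing of vital signs from which these quantities could be rebuilt.

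**Working it through.** The plan gives no figure to reproduce here: the analysis is descriptive and no vital-sign SD or effect is stated. The check is algebra on the definition, a count, and a worked example with assumed values.

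**Definition.** Let pre(k) and post(k) be the readings at Visit k.

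- Planned change at Visit k: post(k) − pre(k).
- Change since first dose: post(k) − pre(3) = [post(k) − pre(k)] + [pre(k) − pre(3)].

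The second bracket is zero at Visit 3. At Visits 4 and 5 it is the carried-over part, and it enters no planned change.

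**Count of readings**, using the three dosing visits of Appendices B and D:

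| Reading after first dose | Planned change? | Refers to the untreated state? |
|---|---|---|
| Visit 3 post | yes | yes |
| Visit 4 pre | no | – |
| Visit 4 post | yes | no |
| Visit 5 pre | no | – |
| Visit 5 post | yes | no |

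Three of five have a change value, one of five has a change from before treatment, and four of five have no change since first dose.

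**Size of a hidden shift (assumed).** If a shift of 5, 10 or 15 units arises after the Visit 3 post-dose reading and persists, the planned change is 0 at all three visits. Change from pre(3) is +5, +10 or +15 at all four readings of Visits 4 and 5.

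**What the visit summaries can and cannot recover.** Assume 8 subjects, systolic pressure in mmHg, and post = pre within each visit. Visit 3 values are 110, 115, 118, 120, 122, 125, 130, 140 (sum 980, mean 122.5).

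- Case A: every subject is +5 at Visit 5, giving 115, 120, 123, 125, 127, 130, 135, 145.
- Case B: six subjects are +5, one goes from 110 to 145 (+35) and one from 140 to 115 (−25). The Visit 5 values are the same set.

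| Visit 5 result | Case A | Case B |
|---|---|---|
| Mean of values | 1020/8 = 127.5 | 127.5 |
| Median of values | (125 + 127)/2 = 126 | 126 |
| SD of values | sqrt(608/7) = 9.3 | 9.3 |
| Range of values | 115-145 | 115-145 |
| Planned change | 0 | 0 |
| Mean change since first dose | 5 | (35 + 6×5 − 25)/8 = 5 |
| SD of change since first dose | 0 | sqrt((30² + 30²)/7) = 16.0 |
| Range of change since first dose | 5 to 5 | −25 to +35 |

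In general the SD of the change cannot be derived from the visit SDs. With equal visit SD s and within-subject correlation r it is s·sqrt(2(1 − r)). For assumed s = 12 this is 14.2, 12.0, 9.3 and 5.4 at r = 0.3, 0.5, 0.7 and 0.9. The tables do not report r.

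**Departure of one subject, with no true change in anyone.**

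- Among the 8 above, the subject at 140 leaves: (980 − 140)/7 = 120.0 against 122.5, a move of −2.5.
- In a placebo group of 3 (assumed 110, 122, 140): (110 + 122)/2 = 116 against 372/3 = 124, a move of −8.0.
- If the three placebo groups are pooled (assumed: the same values three times over, one subject at 140 leaving): 976/8 = 122 against 124, a move of −2.0.

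**The case against.** The best case for leaving the section alone has five parts.

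1. *Carry-over is unlikely.* Section 1.4 reports minimal or no systemic absorption in two clinical pharmacokinetic studies, a half-life in saliva of 18.8 minutes, and half-lives of 1.1 to 3.92 hours after parenteral dosing in rats and dogs. Earlier multiple-dose studies found no clinically significant vital-sign changes (Section 1.1.2), and one of them had a maximum daily exposure of 115.2 mg against up to 54.4 mg here. A same-visit baseline is a reasonable choice for acute effects. This lowers the chance of finding anything, but it does not replace looking, given an objective that names multiple administrations.

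2. *The word baseline elsewhere only labels a visit*, and Section 3 uses it loosely. That is fair: the mismatch does not by itself show that Section 8.7.6.4 is wrong. The gap remains on either reading of the label.

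3. *Group means are visible.* A drift in the mean can be read from the raw table when the same subjects attend, and an acute response that grows with each dose would show. Both points stand. Section 8.7.6.4 also promises only the mean for change, so moving the baseline alone would not supply the SD and range. The fix therefore has to name those statistics.

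4. *The examples are constructed.* Cases A and B match because two subjects were made to trade places, and in most data some tabulated statistic would differ. After a departure, N would show 7 rather than 8 and the maximum 130 rather than 140. The −8.0 needs an unpooled placebo group, and the plan does not say whether placebo is pooled. These points limit the size of the effect. The cancellation and the loss of pairing do not depend on the chosen values.

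5. *Withdrawal readings will be few*, being taken where feasible and only within the safety period. True, but a reading taken for safety reasons should appear somewhere.

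Untoward events are still caught as adverse events (Sections 7.1 and 8.7.6.1), independently of this baseline.

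**Conclusion.** The concern holds. As written, the vital-sign change at Visits 4 and 5 is only the same-visit response, and no section plans a change from the Visit 3 pre-dose value. None places the withdrawal or exit reading in a vital-sign display, and Section 8.7.6.5 leaves only microbiology detail to the SAP. What is lost is the within-subject change since first dose: its spread, its pairing when a subject leaves, and any change value for a withdrawal reading taken away from a dosing visit.

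The conclusion rests on reading the baseline sentence visit by visit, which is its natural sense. If a single Visit 3 baseline was meant, the sentence needs correcting anyway. The mmHg figures are assumed; the count of readings and the algebra are not.

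The weight is moderate. The analysis is descriptive, and adverse events and oral and physical examinations do not use this baseline. The change should be made because it lets the vital-sign analysis address the stated objective at almost no cost.

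**What to change.** In Section 8.7.6.4, add change from the Visit 3 pre-dose value, by treatment group, for:

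- Visit 3 post-dose;
- Visits 4 and 5, pre- and post-dose;
- any withdrawal or early-termination reading.

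State that this change is summarised with the statistics Section 8.1 already lists for continuous variables: "Descriptive summary statistics will include N, mean, standard deviation, median, range (minimum and maximum) for continuous variables". Keep the existing pre-to-post change within each visit and label it acute change, so that the two cannot be confused.

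The cost is one extra table from data already collected. Visits, dosing and data collection do not change.

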8.7.6.5 Microbiology Analysis

All stimulated saliva and dental plaque samples obtained in this study will be tested for *S. mutans* using mitis-salivarius bacitracin (MSB) agar plating. Stimulated saliva and dental plaque samples taken at visits 3 & 6 will be tested for total bacteria testing using Todd Hewitt (TH) agar plating. Dental plaque and stimulated saliva samples will be stored for *S. mutans* and total bacteria testing using quantitative Real-Time Polymerase Chain Reaction (qRT-PCR) and bacterial community analysis. Descriptive statistics utilizing mean, standard deviation, median and range of oral microbes at each time point for each treatment group will be determined and compared to Baseline, as applicable.

Further details regarding the microbiology analysis will be presented in the Statistical Analysis Plan (SAP).

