	
information on the safety and microbiology of multiple administrations of C16G2 Varnish or Placebo. Subjects may be replaced at the Sponsor's discretion.
 
Data Analysis:
 
Analysis Sets: There will be two analysis sets; the safety analysis set and the microbiology analysis set
 
• The safety analysis set will be defined as those subjects who received any amount of study drug (C16G2 Varnish or Placebo)• The microbiology analysis set will be comprised of two subsets, the saliva microbiology and dental plaque microbiology subset. These subsets will be based on the subjects who received study drug and have at least one baseline and one post-baseline dental plaque and saliva sample, respectively. 
Safety:
 
All safety-related interventions, adverse events (AEs), and findings will be summarized. The incidence and duration of treatment emergent AEs (TEAEs) will be summarized by study arm. An AE will be considered treatment emergent if the onset date and time occur on or after the recorded clock time of the administration of study drug (C16G2 Varnish or Placebo). Adverse events will be coded using the Medical Dictionary for Regulatory Activities (MedDRA®). The severity of each adverse event will be determined using the Common Terminology Criteria for Adverse Events (CTCAE) Version 4.0.
 
All adverse events (AEs) will be classified by the relationship of the event to study drug as 1) None, 2) Unlikely, 3) Possible or 4) Probable. All AEs will be followed in accordance with good medical practice until resolved or fully stabilized. All serious AEs (SAEs) will be followed until the outcome is known or the subject's condition has stabilized.
 
Other safety assessments include vital signs, oral cavity assessments, and targeted physical exams. These safety parameters will be presented using descriptive statistics.
 
Microbiology:
 
All stimulated saliva and dental plaque samples obtained in this study will be tested for S. mutans using mitis-salivarius bacitracin (MSB) agar plating. Stimulated saliva and dental plaque samples taken at visits 3 and 6 will be tested for total bacteria testing using Todd Hewitt (TH) agar plating. Dental plaque and stimulated saliva samples will be stored for S. mutans and total bacteria testing using quantitative Real-Time Polymerase Chain Reaction (qRT-PCR) and bacterial community analysis.
 
Descriptive statistics utilizing mean, standard deviation, median and range of S. mutans and total bacteria will be determined and compared to Baseline samples, as applicable.

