Microbiology assessments did not demonstrate an apparent reduction or increase in *S. mutans* and other bacterial species outside of the variation observed in the placebo cohort, indicating that single C16G2 doses formulated as a mouth rinse did not impact the oral microbiome.

Study C3J16-V102-00, a Phase 1, single-blind, randomized, placebo-controlled, dose-escalation study evaluated the safety and efficacy of single 13.6 mg, 27.2 mg, 54.4 mg C16G2 Varnish or Placebo administrations.

The objectives of this study were to evaluate the safety and microbiology of C16G2 Varnish formulation in healthy adult subjects and to assess the targeted antimicrobial activity of C16G2 as measured by a reduction in the number of salivary *S. mutans*. In addition, the study assessed the bacterial composition in the oral cavity over 28 days post single study drug administration in healthy adult dental subjects.

A total of 48 adult healthy subjects were enrolled, of which 30 subjects received C16G2 and 18 subjects received placebo. C16G2 was well-tolerated with no deaths and no other serious or severe AEs. No study drug-related treatment-emergent AEs were reported and no subject was discontinued due to an AE. No clinically significant changes in vital signs were observed in association with the administration of C16G2. Oral cavity assessments and targeted physical exams did not indicate any clinically relevant changes due to study drug administration. Microbiology evaluations demonstrated a significant decrease in *S. mutans* levels in saliva and plaque samples in each dose level. The 27.2 mg dose group showed the greatest decrease in *S. mutans* compared to Placebo and the other two dose groups. Total bacteria levels did not change significantly post study drug administration. The clinical study report for this study is currently in preparation.

1.1.2 Phase 2

To enhance the targeted *S. mutans* killing activity of C16G2 in dental plaque, C3 Jian formulated the drug product for both mouth rinse and gel application. C3J13-201-01, a double-blind, placebo-

controlled study, evaluated different combinations of multiple C16G2 Gel and/or C16G2 mouth rinse administrations at two dose levels. To determine the most effective mode of gel application, gel was applied by manual toothbrush, Sonicare™ toothbrush and upper and lower custom dental trays.

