3.1 Blinding and Randomization

3.1.1 Randomization

The study will enroll subjects into up to three study arms. Up to 33 subjects will receive multiple doses of study drug (27.2 mg and/or 13.6 mg and/or 54.4 mg C16G2 Varnish or Placebo) applied with a small brush typically used in dental varnish administration (for details see Appendix A). Subjects will be enrolled in an 8:3 ratio. The Sponsor will perform unblinded microbiology review on an ongoing basis to determine whether to enroll additional 11 subjects into the next dose cohort (13.6 mg and/or 54.4 mg C16G2 Varnish or Placebo) or to terminate enrollment based on microbiology data.

After confirmation of study eligibility, subjects will be randomized at Visit 3 (Day 0) by authorized study staff according to the master randomization schedule from the Sponsor's study statistician. The randomization schedule and associated documentation will be kept in a secure location at the study site.

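### The protocol compares S. mutans counts only with Baseline, group by group; it states no C16G2-minus-placebo difference, interval, analysis scale or rule for counts below the plating limit

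*Combined protocol and SAP*

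**What the plan says.** - **Objective.** Safety and tolerability are primary. The first secondary objective (Section 2) reads "To assess the targeted antimicrobial activity of C16G2 Varnish applications as measured by a reduction in" *S. mutans* in saliva and plaque. It names no comparator.
- **Design.** Randomised and placebo-controlled, with 8 C16G2 and 3 placebo subjects per dose cohort and up to three cohorts (Sections 3.1.1 and 5).
- **Microbiology analysis.** Section 8.7.6.5 plans mean, SD, median and range, and the only comparison it names is with Baseline: "oral microbes at each time point for each treatment group will be determined and compared to Baseline, as applicable". The synopsis gives the same statistics for *S. mutans* and "total bacteria will be determined and compared to Baseline samples, as applicable".
- **General rule.** Section 8.1: "All statistical analysis will be descriptive in nature". It adds: "Descriptive summary statistics will include N, mean, standard deviation, median, range (minimum and maximum) for continuous variables". No interval or between-group difference is listed.
- **Deferral.** Section 8.7.6.5 leaves further microbiology detail to the SAP. The supplied document contains no separate SAP text.
- **Use of the data.** Under Section 3.1.1 the sponsor's ongoing unblinded microbiology review will "determine whether to enroll additional 11 subjects into the next dose cohort". Section 8.2 places a review after Arm 1 has completed Visit 8.
- **Earlier trials.** Section 1.1.1 judged one earlier trial by whether changes lay "outside of the variation observed in the placebo cohort". Sections 1.1.2 and 1.3 report reductions on the log10 scale.

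**The concern.** A placebo group is randomised so that its experience can be subtracted. Here every subject has prophylaxis and hygiene training at Visit 2, receives fluoride toothpaste and floss, brushes and flosses in the clinic before each dose, and is coated with a varnish. Any shift in counts that these cause after Visit 3 appears in the C16G2 group's change from Baseline as if it were drug effect. The placebo summaries will be tabulated beside it, but the contrast and its precision are left to the eye.

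The scale is open as well. Bacterial counts are strongly skewed, and raw and log10 means can tell different stories. No value is stated for counts below the plating limit, which affects any log10 summary.

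At stake is how the secondary activity objective is read: a group-wise fall might be taken as drug activity, or a noisy difference between small groups over-read, because no interval accompanies it.

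**Working it through.** **1. The plan's own figure.** Three cohorts of 8 + 3 give 3 × 11 = 33, as stated. Section 8.4 says that no data exist for a formal calculation, so there is no power, SD or effect size to reproduce.

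**2. Shared shift.** Let *s* be a shift common to both groups after Visit 3 and *d* the drug effect. The C16G2 change is *d* + *s*, the placebo change is *s*, and the difference is *d*. The shift enters each group's change in full and cancels in the contrast. This needs no SD.

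**3. Scale (invented example).** Seven subjects fall from 10^5 to 10^4 and one stays at 10^7. The raw mean goes from (7 × 10^5 + 10^7)/8 = 1,337,500 to (7 × 10^4 + 10^7)/8 = 1,258,750, a fall of 6%. The mean log10 change is −7/8 = −0.875.

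**4. Precision of a change-score difference.** The 95% half-width is t(0.975, n1 + n2 − 2) × SD × √(1/n1 + 1/n2). The SD of log10 change is assumed: 0.7, range 0.5 to 1.0.

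| Contrast | Half-width in SDs | log10 at 0.7 (0.5 to 1.0) |
|---|---|---|
| 8 v 3, one cohort | t(9) × √(1/8 + 1/3) = 1.531 | 1.07 (0.77 to 1.53) |
| 8 v 6, one later cohort opens | t(12) × √(1/8 + 1/6) = 1.177 | 0.82 (0.59 to 1.18) |
| 8 v 9, all cohorts | t(15) × √(1/8 + 1/9) = 1.036 | 0.72 (0.52 to 1.04) |

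**5. ANCOVA on Visit 3.** The mean half-width over 100,000 simulated bivariate-normal trials per setting, for 8 v 3, is 1.535, 1.394 and 1.151 single-visit SDs at assumed baseline/post correlations of 0.3, 0.5 and 0.7. At a single-visit SD of 0.7 these are 1.07, 0.98 and 0.81 log10. For comparison, the SD of change is 0.7 × √(2(1 − r)) = 0.83, 0.70 and 0.54, so the change-score half-widths (× 1.531) are 1.27, 1.07 and 0.83. ANCOVA is never wider in this range, and its gain is modest unless the correlation is low.

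**6. Chance imbalance at Visit 3, 8 v 3.** The mean absolute difference is √(2/π) × √(1/8 + 1/3) = 0.540 SD, or 0.38 log10 at SD 0.7 (0.27 to 0.54). A comparison of post-dose means that ignores Visit 3 would carry this.

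**7. Can pooling of placebo be checked?** The half-width for placebo against placebo is t(4) × √(2/3) = 2.267 SD (3 v 3) or t(7) × √(1/3 + 1/6) = 1.672 SD (3 v 6). At SD 0.7 that is 1.59 or 1.17 log10, too wide to rule out drift between cohorts.

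**The case against.** The study is openly descriptive, safety is primary, and scale, below-limit counts and contrasts are ordinary SAP content that Section 8.7.6.5 expressly defers. This stands in part. It limits the claim to what the supplied text states, and a reader who inferred that no placebo comparison is planned anywhere would go too far. Nor is the lack of a hypothesis test a fault: it is a declared choice, and a difference with an interval is estimation.

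Readers can also do the subtraction. With complete data, the difference in change between groups follows from the planned visit-by-group means and already corrects for Visit 3 imbalance, on whatever scale is tabulated. It would therefore be wrong to infer that no baseline-corrected estimate can be recovered. What cannot be recovered is its interval, unless SDs of change are tabulated, or an ANCOVA estimate.

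The shared shift has no size in the documents. Prophylaxis takes place 2 to 7 days before Visit 3, so part of its effect is already in Baseline, and regrowth could move counts upward. This stands: the argument is structural and gives no bias figure.

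Finally, up to 5 visits × 2 sample types × 3 doses × 2 placebo sets = 60 intervals for *S. mutans* would invite selective reading, each wide against the roughly 1 log10 suppression cited in Section 1.3. This stands too, and is why one key visit should be named.

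**Conclusion.** The point holds for the supplied text, as a cheap improvement of minor to moderate weight. In a randomised placebo-controlled trial, the stated analysis does not include the contrast that answers the activity objective, its precision or its scale. The cancellation of shared shifts is exact. The half-widths rest on assumed SDs and correlations, and for 8 v 3 come to about 1 log10 at SD 0.7.

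Two further inferences are not supported:

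- A reader might conclude that the cohort-opening decision is compromised by Section 8.7.6.5. That decision comes from separate sponsor reviews (Sections 3.1.1, 8.2 and 8.6), and under Section 3.1.1 the reviewers are unblinded and so can see placebo results. Changing the end-of-study tables alone does not reach it.
- A reader might conclude from Section 5.1.1 that the placebo lacks some of the active vial's excipients, so that the contrast cannot isolate the peptide. The section says that two excipients are shared, but gives no count for the active vial and refers composition to the Investigator's Brochure.

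**What to change.** In Section 8.7.6.5 and the synopsis:

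- Analyse log10 CFU, saliva and plaque separately, and state the value given to counts below the plating limit.
- Report each dose minus placebo with a 95% CI from ANCOVA on the Visit 3 pre-dose log10 count, labelled exploratory and without tests.
- Name Visit 6 as the key visit and tabulate Visits 7 to 10 as supportive. With Visit 3, Visit 6 is already the visit chosen for total bacteria.
- Show the within-cohort contrast (8 v 3). If later cohorts open, add the pooled-placebo contrast as secondary, stating that pooling assumes no drift between cohorts.

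Amend Section 8.1 to read: descriptive, with 95% CIs for exploratory contrasts. If the contrast is meant to inform the cohort decision, cite it also in Sections 3.1.1 and 8.2. If the SAP already holds these items, a cross-reference and the Section 8.1 wording are enough.

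**Cost.** Analysis wording and additional tables, with no new samples or visits. With Visit 6 as key, the within-cohort set is at most 3 doses × 2 sample types = 6 key intervals. The downside is that these are visibly wide, and that the pooled contrast rests on an assumption this study cannot verify.
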